#### Serious adverse event (SAE)

A serious adverse event (SAE) is one that at any dose (including overdose):

- results in death
- is life-threatening
- requires subject hospitalization or prolongation of existing hospitalization
- results in persistent or significant disability/incapacity or
- is a congenital anomaly/birth defect
- is an important medical event.

#### Comment:

Death is an outcome of an event. The event that resulted in death should be recorded and reported as an SAE.

“Life-threatening” means that the subject was at immediate risk of death at the time of the serious adverse event; it does not refer to a serious adverse event that hypothetically might have caused death if it were more severe.

If the admission is pre-planned (i.e., elective or scheduled surgery arranged prior to start of the trial) or not associated with an adverse event (e.g., social hospitalisation for purpose) or results in a hospital stay less than 12 hours, the serious criterion “hospitalisation” is not fulfilled. However, it should be noted that invasive treatment during a hospitalisation may fulfil the criteria of “medically important” and may be reportable as a serious adverse event dependent on clinical judgement.

An inpatient rehabilitation program per se does not fulfil the seriousness criterion “hospitalization”. In this case the investigator should evaluate carefully whether the reason for the inpatient rehabilitation program has to be documented as an AE/ SAE.

“Persistent or significant disability or incapacity” means that there is a substantial disruption of a person’s ability to carry out normal life functions. The irreversible injury of an organ function (e.g., paresis, diabetes, cardiac arrhythmia) fulfils this criterion.

Medical and scientific judgement should be exercised in deciding whether expedited reporting is appropriate in situations where none of the outcomes listed above occurred. Important medical events that may not be immediately life-threatening or result in death or hospitalization but may jeopardize the subject or may require intervention to prevent one of the other outcomes listed in the definition above should also usually be considered serious. Examples of such events include allergic bronchospasm requiring intensive treatment in an emergency room or at home, convulsions that do not result in subject hospitalization, or the development of drug dependency or drug abuse. A diagnosis of cancer during the course of a treatment should be considered as medically important.

#### Clarification of the onset and end date of AEs and SAEs

The onset date of the AE is defined as the onset of signs and symptoms or a change from baseline. The onset date of the SAE is defined as the date the signs and symptoms/diagnosis became serious, i.e., met at least one of the ICH criteria for seriousness.

The end date of the AE is defined as the date when the symptoms resolve, or the event is considered stable. The end date of the SAE is defined as the time the seriousness criteria are no longer applicable. The end date of the SAE must not be later than the end date of the corresponding AE. AEs and SAEs that are on-going at the time of death are considered not resolved or resolving.

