### 7.3 Period of observation

In this trial, the period of observation for collection of adverse events extends from signing the informed consent up to the end of trial. If the investigator detects a serious adverse event in a trial subject after the end of the period of observation, and considers the event possibly related to the prior trial, he should contact the sponsor to determine how the adverse event should be documented and reported.

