### 7.4 Documentation of AEs and Follow up

All AEs (whether serious or not) reported by the subject or detected by the investigator will be documented on the appropriate pages of the case report form (CRF). AEs must also be documented in the subject's medical records. If the adverse event is serious (see Section 7.1), the investigator must complete, in addition to the "Adverse Event Page", a "Serious Adverse Event Form" at the time the serious adverse event is detected.

Every attempt should be made to describe the adverse event in terms of a diagnosis. If a clear diagnosis has been made, individual signs and symptoms will not be recorded unless they represent atypical or extreme manifestations of the diagnosis, in which case they should be reported as separate events. If a clear diagnosis cannot be established, each sign and symptom must be recorded individually.

All subjects who have adverse events, whether considered associated with the use of the investigational products or not, must be monitored to determine the outcome. The clinical course of the adverse event will be followed up according to accepted standards of medical practice, even after the end of the period of observation, until a satisfactory explanation is found or the investigator considers it medically justifiable to terminate follow-up, but no longer than 90 days after the end of the trial.

Should the adverse event result in death, a full pathologist's report should be supplied, if possible.

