4.2.1 Efficacy

The following variables will be investigated:

- Oxygen saturation (O2-sat, in room air) (only absolute, as relative already primary outcome) assessed at every visit (not web/tele feedback)
- Respiratory rate (RR, in room air) (relative and absolute) assessed at every visit and every web/tele feedback
- Retractions (yes/no) assessed at every visit and every web/tele feedback
- Coughing last 24 h (yes/no) assessed at every visit and every web/tele feedback
- Oxygen requirement assessed at every visit and every web/tele feedback
- pO2, pCO2 (capillary, in room air)
- Chest x-ray scoring for chILD assessed at screening and visit 3 (START HCQ Block) and visit 5 (STOP HCQ Block)
- Overall survival
- If > 5y old
 - FEV1 % predicted (recorded in L)
 - FVC % predicted (recorded in L)
 - reference values according to the GLI 2012 lung function regression equations
 - 6 minutes walking distance (meter)
 - O2-saturation before and after 6MWT
 - Borg scale
- If ventilated:
 - Duration (h) of mechanical ventilation
 - NO (%), ECMO yes/no, if yes VA/VV, double lumen vs. single lumen, Flow-rate.

4.2.2 *Safety/Tolerability*

Adverse events, clinical laboratory values (GOT, Creatinine, gGT, blood count, differential, LDH, BNP, steady state drug level), ECG, ophthalmologic review

Adverse events will be documented during the study at each visit (exemption: START HCQ between Visits 1 and 2. However, occurring AEs between those visits are not treatment emergent).

Laboratory data will be assessed at screening, visit 3 and visit 4 in the START HCQ Block and at screening, visit 3, 4 and visit 5 and EDTA additionally at visit 6 in the STOP HCQ Block.

Vital signs (respiratory rate, height, weight, BMI, heart rate, blood pressure (systolic and diastolic), temperature, hypoglycaemia (yes/no), appropriate observation of blood glucose levels (yes/no), cardiotoxicity (yes/no), appropriate ECG (yes/no)) will be assessed at screening, and every following visit (not web/tele feedback).

A physical examination will be done at the same visits.

Symptoms and clinical course of treatment will be documented at the same time points as the physical examination is performed and at telephone contact visit.

4.2.3 *Quality of Life (Peds QL)*

Not applicable.

4.2.4 *Health Economics*

Not applicable.

5 Treatment of Missing Values and Outliers

5.1 *Missing Values*

No substitution of missing values is planned.

5.2 *Outliers*

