6.7.2 Safety/Tolerability

6.7.2.1 Adverse Events

Only treatment emergent adverse events (AEs) will be analysed. These are adverse events that occurred after taking study medication. In particular this means only the following events are considered as treatment emergent:

START BLOCK: Events starting at visit 2 or later

STOP BLOCK: Events starting at visit 1 or later

In case of missing start data, adverse events are considered as treatment emergent.

Frequencies of subjects experiencing at least one AE will be displayed by body system and preferred term according to MedDRA terminology. Detailed information collected for each AE will include: A description of the event, duration, whether the AE was serious, intensity, relationship to trial drug, action taken, and clinical outcome.

Summary tables will present the number of subjects observed with AEs and corresponding percentages. Additional subcategories will be based on seriousness of event, event intensity and relationship to trial treatment.

An overview table will be produced showing the number of patients with

- any AEs
- any SAEs
- any deaths
- any severe AEs
- any related AEs
- any related severe AEs
- any related serious AEs
- any fatal related AEs
- any AEs leading to premature study discontinuation

A subject listing of all AEs will be prepared.

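### SAP 6.7.2.1 has no rule for START adverse events that begin before Visit 2 and then worsen or become serious on trial medication

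*Protocol*

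**What the plan says.** SAP 6.7.2.1 limits the AE analysis: "Only treatment emergent adverse events (AEs) will be analysed. These are adverse events that occurred after taking study medication". It then closes the definition: "In particular this means only the following events are considered as treatment emergent". For START the list has one entry, "START BLOCK: Events starting at visit 2 or later". For STOP, events count from Visit 1. An event whose start date is missing is counted. SAP 4.2.2 confirms the START rule for the interval between Visits 1 and 2: "occurring AEs between those visits are not treatment emergent".

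Protocol 7.1 has two onset rules. For an AE: "The onset date of the AE is defined as the onset of signs and symptoms or a change from baseline". For an SAE: "The onset date of the SAE is defined as the date the signs and symptoms/diagnosis became serious". The same section does not allow an SAE to end later than its corresponding AE, and protocol 7.4 requires an SAE form on top of the AE page. The SAE is thus a stage within one AE, and that AE carries two start dates.

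On collection, protocol 7.3 states that "the period of observation for collection of adverse events extends from signing the informed consent up to the end of trial", and protocol Table 1-1 marks AEs at the START screening visit. Protocol 8.4 plans AE summaries for the safety population and states no treatment-emergent restriction.

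**The concern.** A treatment-emergent rule should keep events in which trial medication may have made an existing problem worse. The START rule looks only at when an event started. It is silent on an event that was mild in screening and became severe or serious after dosing, and it leaves open which of the protocol's two dates it means. Two programmers could follow the SAP correctly and report different SAE counts from the same data.

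Safety of HCQ after 28 and 56 days is a stated secondary objective of START. If HCQ aggravates problems that arose in screening, the events at risk of leaving the tables are those that would show it.

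**Working it through.** No arithmetic decides the point, so the check applies the SAP rule to a test case.

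**Inputs.** START screening runs from Day -28 to Day -3, and Visit 2 is Day 1 (protocol synopsis, Table 1-1). The onset rules are in protocol 7.1 and the treatment-emergent rule in SAP 6.7.2.1.

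**Test case.** A child in START has an AE that first appears on Day -10 and worsens on Day 15.

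1. *It becomes serious, and the AE onset date is used.* Day -10 precedes Visit 2. The event is not treatment emergent and is missing from the incidence tables and from the overview rows for SAEs and related events.
2. *It becomes serious, and the SAE onset date is used.* Day 15 follows Visit 2, so the SAE is counted.
3. *It becomes severe but not serious.* The protocol gives no second onset date for a change in intensity. The event drops out of the row for severe AEs and the related-event rows unless it is re-entered as a new AE.
4. *The site enters the worsening as a new AE, or the start date is missing.* The event is counted.
5. *The same event occurs in STOP screening.* It is always counted, because the STOP rule begins at Visit 1.

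**Is re-entry as a new AE assured?** Protocol 7.1 lists worsening of a condition that existed before the trial as a possible AE. Protocol 7.10.1 treats illness known at consent as medical history and illness detected during the trial as an AE. Worsening of a known illness can therefore be a new AE with an on-treatment start. An illness that first arises after consent is already an AE, and no text tells the site to open a second record when it worsens. The gap is confined to this group.

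**Collection in START screening.** Protocol 7.3 and Table 1-1 collect AEs from consent. SAP 4.2.2 exempts the interval between Visits 1 and 2 from documentation, and the SAP's START schedule has no AE mark at Visit 1. The two documents disagree.

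**Tables or listings.** SAP section 6 says that AE data will be given as listings only. SAP 6.7.2.1 plans incidence tables, subcategory tables and an overview table. Both cannot stand.

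**Sensitivity to one event.** With the planned 80 subjects split equally between blocks and 1:1 between arms, START has 80/2 = 40 children and 40/2 = 20 per arm. One child moved in or out of an overview row changes that arm's percentage by 1/20 = 5 points. This shows how much one case weighs, not how many cases to expect.

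**The case against.** A reader might infer that on-treatment SAEs that began in START screening can never be treatment emergent and vanish from all AE output. The documents do not support that.

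- The SAP does not name the date field. Under the SAE onset rule of protocol 7.1 the serious event is counted. The AE onset rule also mentions a change from baseline, which some would apply to worsening on treatment.
- The conflict between two dates concerns seriousness only. For intensity the fault is the missing worsening clause.
- A subject listing of all AEs is planned, and with about 40 START children it can be read case by case.
- Deaths enter overall survival from randomisation, whatever the AE start date, although not as fatal related AEs.
- Protocol 7.1 keeps progression of the lung disease out of AE reporting unless it is fatal, and protocol 7.5 has it reported if it meets the SAE definition. Non-serious aggravation of the disease therefore leaves the AE data by that route. START also requires stability between Visits 1 and 2.
- The rule is the same in both arms, so the comparison to Day 28 is not obviously biased.

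A reader might also infer that screening AEs were never recorded. Sites work to the protocol, which collects them from consent, so the SAP text shows a mismatch and not lost records. Nor can a size be built from assumed AE rates: that would give the share of children with an AE ongoing at the first dose, not the share whose event then worsens.

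These arguments narrow the point but do not remove it. The START list is closed, no worsening clause exists, and the choice of onset date decides whether a serious event is counted.

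**Conclusion.** The point holds in limited form. For START, an AE that first arises between consent and Visit 2 and intensifies on trial medication is left out of the treatment-emergent summary tables unless it is re-entered as a new AE. If it becomes serious on treatment, the SAE count depends on an onset date that the SAP does not specify. The gap applies to both arms and is not specific to HCQ. Its size cannot be estimated, because the documents give no AE rates and no share of events that worsen. The conclusion assumes that the tables of SAP 6.7.2.1 will be produced; if the listings-only sentence governs, there is no table for the events to leave. This should be corrected, because a stated rule gives a poorer safety summary and the remedy is small.

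**What to change.** In SAP 6.7.2.1, for START: *An AE is treatment emergent if its onset, an increase in its intensity, or its becoming serious (SAE onset as in protocol 7.1) falls on or after the first dose of trial medication.*

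For STOP, add the same worsening and seriousness clause and keep the Visit 1 start, or justify any change to it. A first-dose cut-off applied to both blocks would silently drop STOP screening events that are now counted.

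Reconcile two further places:
- the START documentation exemption in SAP 4.2.2 and the blank Visit 1 cell in the SAP schedule, with AE collection from consent in protocol 7.3 and Table 1-1;
- the listings-only sentence in SAP section 6, with the tables in SAP 6.7.2.1.

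The cost is SAP wording and one derivation rule, settled before unblinding. The rule needs a date for an increase in intensity. The documents do not show whether the AE page holds one, so a blinded read of the AE listing may be needed for those cases. The downside is that some natural worsening of screening illnesses will be counted, under the same rule in both arms.

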#### Clarification of the difference in meaning between “serious” and “severe”:

The terms “serious” and “severe” are not synonymous but are often used interchangeably. The term ‘severe’ is often used to describe the intensity (severity) of a specific event; the event itself, however, may be of relatively minor significance (such as severe headache). This is not the same as “serious”, which is based on subject/event outcome or action criteria usually associated with events that pose a threat to a subject’s life or functioning. Seriousness (not severity) serves as a guide for defining regulatory reporting obligations.

#### Suspected Unexpected Serious Adverse Reaction (SUSAR)

A SUSAR is every SAE with an at least possible relationship to the investigational medicinal product which is unexpected. An unexpected serious adverse reaction is any adverse reaction, the nature or severity of which is not consistent with the applicable product information of the current country specific Summary of Product Characteristics of Hydroxychloroquinsulfate (SmPC)).

## 7.2 Assessment of AEs by investigator

Subjects must be carefully monitored for adverse events by the investigator. The intensity of the adverse events and the causal relation to trial medication and/or procedures are to be assessed.

### Intensity/ Severity

The intensity of an AE will be assessed by the investigator as follows:

Mild:      Temporary event which is tolerated well by the subject and does not interfere with normal daily activities.

Moderate:   Event which results in discomfort for the subject and impairs his/her normal activity.

Severe:      Event which results in substantial impairment of normal activities of subject.

If the event is serious, the severity reported in the adverse event must be consistent with the severity included in the adverse event report.

### Causal relation to trial medication/procedures

The assessment of the relationship of an adverse event to the administration of study drug is a clinical decision based on all available information at the time of the documentation. Factors to be considered in assessing the relationship of the adverse event to study drug include:

- The temporal sequence from drug administration: The investigator has to consider, if the event occurred before first intake of study medication or long time after last intake. Additionally the length of time from drug exposure to event should be evaluated in the clinical context of the event.
- Recovery on discontinuation (de-challenge), recurrence on reintroduction (re-challenge): Subject's response after drug discontinuation (de-challenge) or subjects response after drug re-introduction (re-challenge) should be considered in the view of the usual clinical course of the event in question.
- Underlying, concomitant, intercurrent diseases: Each report should be evaluated in the context of the natural history and course of the disease being treated and any other disease the subject may have.
- Concomitant medication or treatment: The other drugs the subject is taking or the treatment the subject receives should be examined to determine whether any of them may be suspected to cause the event in question.

Positive causal relationship:

An assessment of 'related' implies a reasonable possibility of a causal relationship between the event and the investigational medicinal product (IMP).

This means that there are facts (evidence) or arguments to suggest a causal relationship, such as:

- A close temporal relationship
- A common drug reaction to the IMP
- No plausible alternative cause

Negative causal relationship:

An assessment of 'not related' means that there is no reasonable possibility of a causal relationship between the event and the investigational medicinal product.

This includes for example:

- Another cause of the adverse event is more plausible
- A temporal sequence cannot be established with the onset of the adverse event and administration of the study treatment
- A causal relationship is considered biologically implausible.

### 7.3 Period of observation

In this trial, the period of observation for collection of adverse events extends from signing the informed consent up to the end of trial. If the investigator detects a serious adverse event in a trial subject after the end of the period of observation, and considers the event possibly related to the prior trial, he should contact the sponsor to determine how the adverse event should be documented and reported.

### 7.4 Documentation of AEs and Follow up

All AEs (whether serious or not) reported by the subject or detected by the investigator will be documented on the appropriate pages of the case report form (CRF). AEs must also be documented in the subject's medical records. If the adverse event is serious (see Section 7.1), the investigator must complete, in addition to the "Adverse Event Page", a "Serious Adverse Event Form" at the time the serious adverse event is detected.

Every attempt should be made to describe the adverse event in terms of a diagnosis. If a clear diagnosis has been made, individual signs and symptoms will not be recorded unless they represent atypical or extreme manifestations of the diagnosis, in which case they should be reported as separate events. If a clear diagnosis cannot be established, each sign and symptom must be recorded individually.

All subjects who have adverse events, whether considered associated with the use of the investigational products or not, must be monitored to determine the outcome. The clinical course of the adverse event will be followed up according to accepted standards of medical practice, even after the end of the period of observation, until a satisfactory explanation is found or the investigator considers it medically justifiable to terminate follow-up, but no longer than 90 days after the end of the trial.

Should the adverse event result in death, a full pathologist's report should be supplied, if possible.

### 7.5 Immediate reporting of SAEs by investigator

SAEs must immediately (within 24 hours of the investigator's awareness) be reported to:

**IZKS Mainz  
[name]  
[name]  
[contact]**

The initial SAE Report should be as complete as possible including the essential details of subject's identification (screening number, random number), the serious adverse event (medical term, diagnosis), the trial medication and the assessment of the causal relationship between the event and the trial medication. The SAE report must be reviewed and signed by the investigator. The investigator should provide related additional information on the clinical course and the outcome of each SAE as soon as possible (Follow up report). The "Serious Adverse Event Form" will be provided.

Worsening of a sign or symptom of the condition under treatment will normally be measured by efficacy parameters. However, if the outcome fulfils the definition of "serious adverse event", it must be reported as such.

